5 TRIAL EVALUATIONS

6.1 PRIMARY TRIAL ENDPOINTS

The primary trial endpoint is one -year survival in the absence of Aneurysm Related Complications (ARC). ARC is a composite of the most relevant EVAR related outcomes and includes:

- Peri-operative death (< 30-days)
- Aneurysm rupture
- Conversion to Open Surgical Repair (OSR)
- Endoleaks; post-operative
- Endograft migration (≥ 10mm)
- Aneurysm enlargement (≥ 5mm compared to 1-month CT)
- Endograft occlusion
- Reinterventions for device- or aneurysm-related complications

The outcomes above comprising of the ARC composite endpoint are defined in §12.1.

Imaging driven observations will be based on the one-year evaluation window (365 days \pm 60 days). If there are two diagnostic images available within the window, the convention will be to use any image with a positive finding.

6.2 SECONDARY TRIAL ENDPOINTS

Secondary endpoints to be assessed up to five years include:

- 1. Major Adverse Events (MAEs) at 30-Days, 12-Months and annually thereafter, up to five years:
 - Mortality (all-cause)
 - Bowel Ischemia
 - Myocardial Infarction
 - Paraplegia
 - Renal Failure
 - Respiratory Failure
 - Stroke
 - Procedural Blood Loss ≥1,000mL
- 2. ARC post 12-Months
- 3. Individual components of ARC post 12-Months and up to five years
- 4. Aneurysm Related Mortality
- 5. Endoleaks Classified by Type
- 6. AAA Related Secondary Procedures
- 7. Device Integrity
- 8. Any adjunctive procedures necessitated during the implant procedure

7 ADDITIONAL EVALUATIONS

Additional evaluations include the following procedural and in-hospital evaluations:

1. Procedural Technical Failure

- 2. Total Endovascular time; from catheter introduction to catheter removal
- 3. Anesthesia Time
- 4. Fluoroscopy Time
- 5. Contrast Volume used
- 6. Total Procedure Time; from cut-down to closure
- 7. Time in ICU
- 8. Total Radiation Exposure

The procedural technical failure is defined as a failure of the AFX® System or comparator devices to be delivered and deployed, such that the procedure is not completed, or the device failure results in a serious complication, or residual Type I and Type III Endoleaks which occur and cannot be resolved during the index procedure.

8 ELECTRONIC CASE REPORT FORMS

The trial will utilize an electronic Case Report Form (eCRF) system for data collection. All site staff will be trained on correct eCRF completion prior to site activation. Only trained personnel will receive access and be able to enter data in the eCRF. All eCRF pages will be electronically signed by the Investigator at each site. Each subject will be anonymized and given a specific trial number in the eCRF.

9 DATA MANAGEMENT

The data required for the trial will be entered by the investigation sites into eCRF. Detailed edit checks will ensure a high-quality standard of the data entered in the database. Additionally, data management will review the collected data and issue possible queries. Queries should be resolved by the investigation site on an ongoing basis. When all trial data is complete, the database will be locked, and data analyzed.

10 STATISTICAL CONSIDERATIONS

10.1 GENERAL CONSIDERATIONS

Primary analyses will be based on modified Intention-to-Treat (mITT) populations. An Intention-to-Treat (ITT) analysis population consists of all randomized subjects. While the intent of the trial is to implant all randomized subjects, some randomized subjects will not undergo implantation due to unforeseen issues. If this were to occur in a substantial number of subjects, it is possible that the results may be biased towards non-inferiority as the groups would become increasingly similar. Thus, a mITT population is defined, which consists of all randomized subjects that subsequently underwent EVAR. All endpoints in this trial, unless otherwise specifically noted, will be evaluated against the mITT analysis population.

Randomization will be centralized using permuted block design. A randomization schedule will be generated with a random number generator in the SAS System[®]. Sites/Investigators will be blinded to block size. Due to the use of a large number of sites with a relatively small number of patients within specific sites, stratification by institution will not be performed. The intent is to allocate similar numbers of subjects between the two treatment groups across the total number of sites, to provide maximum power. Additionally, stratification using risk factors will not be performed.

Additional information is available in the Statistical Analysis Plan (SAP). Statistical analyses will be performed using SAS System®, Version 9.4 or later.

For additional information on the randomization process, refer to §5.6.

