5.6 ENROLLMENT AND RANDOMIZATION

Patient enrollment into this trial is based on the site evaluation of patient conformance with the protocol-specified selection criteria (see §5.1), and the Investigator's assessment of suitability for treatment with either the AFX-System or the comparator device. Blood work and physical exam will also be collected as per standard of care at each institution.

Once consented and assessed for inclusion in the trial, the Investigator will elect to randomize the patient by entering required information into the EDC. Upon entering this information, the patient will be randomized to receive the AFX® System or the comparator device. The randomization result will be generated and accessible to the site prior to the scheduled procedure date.

Enrollment in the trial only occurs upon advancement of the trial device into the subject's vasculature.

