10.2.1 DISTRIBUTION OF THE PATIENTS

The number of patients in the mITT population, as well as the distribution across sites will be presented. Descriptive statistical data will be used to draw up the characteristics of subjects at the time of enrollment (demographics, baseline data).

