12 DEFINITIONS

12.1 DEFINITIONS ASSOCIATED WITH THE COMPOSITE PRIMARY ENDPOINT ARC

The primary trial endpoint is an assessment at one year, where survival is in the absence of Aneurysm Related Complications (ARC). ARC is a composite of the most relevant EVAR related outcomes and include:

- *Aneurysm Rupture*: bleeding or leaking of blood from the aneurysm subsequent to the index procedure.
- Conversion to Open Surgical Repair (OSR): open surgical repair of the abdominal aortic aneurysm due to unsuccessful delivery or deployment of the stent graft, due to complications or other clinical situations that precluded successful endovascular treatment, or at any time following initial successful endovascular treatment for any reason. Excludes post-mortem explant of the trial device.
- Endoleaks: clear evidence of contrast within the aneurysm sac
 - **Endoleak Type Ia** Contrast material in the aneurysm sac adjacent to the proximal seal zone and/or between the endograft and the inner wall of the proximal attachment site.
 - **Endoleak Type Ib** Contrast material in the aneurysm sac adjacent to the distal seal zone and/or between the endograft and the inner wall of the distal attachment site.
 - **Endoleak Type II** Contrast material along the posterior sac wall with visualization of lumbar artery or the inferior mesenteric artery

LEOPARD AAA US Post-Market Trial

- Endoleak Type IIIa Component disconnect
- Endoleak Type IIIb Mid-graft hole
- *Migration* (≥10mm): stent distal movement ≥10mm from the original implant location relative to the center of the distal renal artery; as compared to the 1-month CT scan location.
- Aneurysm Sac Enlargement: aneurysm sac diameter increase of ≥5mm in late followup as compared to 1-month CT scan location.
- *Endograft Limb Occlusions*: defined as total obstruction of blood within the lumen of a device limb irrespective of whether a secondary intervention is necessary.
- *Endograft Stenosis:* defined as a reduction in lumen >50% by, for example, thrombus, intimal hyperplasia, or endograft kink/twist.

Elaboration of the above definitions can be found in the Adjudication Charter.

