12.4 OTHER DEFINITIONS

- Luminal Thrombus Requiring Intervention: any endovascular surgical intervention after completion of the device implantation for resolution of endograft thrombosis.
- *Distal Ischemia*: new onset of compromised peripheral blood flow resulting in femoral or peripheral arterial occlusion or stenosis (attributable to the index procedure or to the endograft and not related to natural progression of atherosclerotic disease) causing a threat to the viability of the limb and requiring surgical or percutaneous intervention; or stent graft occlusion requiring any intervention.
- Occlusion requiring intervention: intervention for stent graft occlusion
- Secondary Endovascular Procedure: any non-diagnostic intervention after the index procedure intended to correct or repair an Endoleak, device stenosis or occlusion, migration, aneurysm sac expansion and/or a device defect (including infection);
- Successful Implantation: Successful delivery and deployment of the device.
- *Modified Intention-to-Treat:* analysis of the results of implanted patients is based on the initial treatment assignment and not on the treatment eventually received.

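### Who enters the mITT set is settled after the site knows the assigned arm, and the supplied text plans neither a by-arm account of patients left out nor an all-randomised analysis

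*Combined protocol and SAP*

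**What the plan says.** Section 10.1 of the combined protocol and SAP defines ITT as everyone randomised, then moves the primary analysis to a narrower set: "a mITT population is defined, which consists of all randomized subjects that subsequently underwent EVAR". It continues: "All endpoints in this trial, unless otherwise specifically noted, will be evaluated against the mITT analysis population". No exception for an ITT analysis appears in the supplied text. The reason given is dilution by patients who are not implanted: "it is possible that the results may be biased towards non-inferiority as the groups would become increasingly similar".

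On sequence, section 5.6 states: "The randomization result will be generated and accessible to the site prior to the scheduled procedure date". Sections 5.4 and 5.6 count a patient as enrolled only once the device enters the body. The only masking described is in section 10.1: "Sites/Investigators will be blinded to block size".

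On reporting, section 10.2.1 says: "The number of patients in the mITT population, as well as the distribution across sites will be presented". Section 10.2.2 counts missing values within mITT. The log in section 5.3 concerns assessment for inclusion, not losses after randomisation.

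Section 12.4 words mITT differently: "analysis of the results of implanted patients is based on the initial treatment assignment and not on the treatment eventually received". Section 12.1 counts open repair after failed delivery or deployment as a conversion, and so as a failure on the primary endpoint.

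**The concern.** Randomisation makes the arms comparable as randomised. Here a later event, EVAR done or not, decides who is analysed, and the people who influence that event can already see the assigned device. If more poor-prognosis patients drop out before EVAR in one arm, that arm looks better than it is. Loss from AFX can produce a false finding of non-inferiority; loss from control can hide a true one. The superiority step in section 10.2 uses the same set.

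A reader of the planned report could not tell a negligible effect from a material one, because the numbers and reasons by arm are not among the planned outputs.

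The two wordings of mITT add a smaller problem. Under section 10.1 a patient whose device could not be delivered and who was converted to open repair can be read as having undergone EVAR. Under section 12.4 the same patient may not count as implanted, and a primary-endpoint failure would leave the analysis.

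**Working it through.** **The plan's own figure.** Section 10.2 gives 86% success for AFX, an 8-point advantage over control (so 78%), one-sided alpha 0.05, and 410 evaluable patients (205 per arm). The margin is 8 points. With the unpooled normal approximation:

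- SE = √[(0.86×0.14 + 0.78×0.22)/205] = 0.0377
- Power = Φ[(0.08 + 0.08)/0.0377 − 1.645] = 99.5%, against the stated 99%. It reproduces.

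**Inputs for the exclusion check.**

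- From the plan: control success 78%, margin 8 points, one-sided alpha 0.05, 10% dropout.
- Assumed: 240 randomised per arm. With 24 exclusions this leaves 480 − 24 = 456, close to the 455 enrolled.
- Assumed: the split of exclusions by arm and the share g of excluded patients who are failures. The documents give neither.

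**Formulas.** With R randomised, e excluded and true all-randomised success p in an arm:

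- mITT success p′ = [R·p − e(1 − g)]/(R − e)
- evaluable n = 0.9(R − e)
- chance of declaring non-inferiority = Φ[(p′_AFX − p′_control + 0.08)/SE − 1.645]

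**False non-inferiority.** The true all-randomised rates are 70% AFX and 78% control, exactly at the margin, so the chance should be 5%.

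| Excluded AFX / control | Excluded patients' outcome | mITT AFX | mITT control | Difference (points) | Chance |
|---|---|---|---|---|---|
| 16 / 8 | all failures | 168/224 = 75.0% | 187.2/232 = 80.7% | −5.7 | 14.0% |
| 16 / 8 | half failures | 160/224 = 71.4% | 183.2/232 = 79.0% | −7.5 | 6.2% |
| 16 / 8 | same risk as own arm | 156.8/224 = 70.0% | 180.96/232 = 78.0% | −8.0 | 5.0% |
| 16 / 8 | 26% failures in both arms | 156.16/224 = 69.7% | 181.28/232 = 78.1% | −8.4 | 4.1% |
| 18 / 6 | all failures | 168/222 = 75.7% | 187.2/234 = 80.0% | −4.3 | 22.7% |
| 18 / 6 | half failures | 159/222 = 71.6% | 184.2/234 = 78.7% | −7.1 | 7.6% |
| 12 / 12 | all failures | 168/228 = 73.7% | 187.2/228 = 82.1% | −8.4 | 4.0% |

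First row in full: SE = √[0.75×0.25/201.6 + 0.807×0.193/208.8] = 0.0409, and Φ[(−0.0569 + 0.08)/0.0409 − 1.645] = Φ(−1.08) = 0.14. The 26% in the fourth row is the average of the two arms' failure rates, 30% and 22%.

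**The other direction.** Let both arms truly have 78% success, with 8 AFX and 16 control patients excluded, all failures. Then mITT is 187.2/232 = 80.7% against 187.2/224 = 83.6%, a difference of −2.9 points. With SE 0.0378 the chance of declaring non-inferiority is 39%. With no exclusions (216 evaluable per arm, SE 0.0399) it is 64%.

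**The case against.** The dilution argument in section 10.1 is sound for a non-inferiority trial. It can be checked with 205 treated patients per arm and a true −8 points among them: if 2%, 5% or 10% of both arms were untreated with equal outcomes, an all-randomised test would declare non-inferiority 5.4%, 6.1% or 7.4% of the time. Those rates are of the same order as the half-failures rows above. This stands, and it is why mITT should remain the primary set.

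The route out of the set is also narrower than it first looks. Section 5.6 requires suitability for either device to be judged before randomisation. A patient who receives a different EVAR device still had EVAR and is analysed as assigned. Only patients with no EVAR at all are lost. This stands too.

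Four stronger readings are tempting and are not supported:

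- A reader might infer that the plan contradicts itself by excluding open repair before any EVAR attempt while section 12.1 counts open repair "due to complications or other clinical situations that precluded successful endovascular treatment". That wording defines a conversion, which most naturally means leaving an endovascular repair. Section 12.1 also places rupture after the index procedure, and section 10.2 sets day 0 at implantation. Rupture while waiting is therefore not an event under the plan as written.
- A reader might take 14% or 23% as the expected error rate. Those figures need every excluded patient to be a failure and a 2:1 or 3:1 imbalance that has no source in the documents.
- A reader might infer that no all-randomised analysis exists anywhere. Section 10.1 refers to a SAP for further information, and no separate SAP text was available, so one cannot be ruled out.
- The revision log dates the move to mITT to August 2021, after enrolment closed and after the unplanned futility analysis. A reader might infer that results drove the change. The documents do not show that, and counting enrolment at device insertion already tied the trial population to the procedure.

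The superiority step carries little practical weight, since section 10.2 says enrolment ended after superiority was judged futile. It does remain in the plan.

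**Conclusion.** The point holds as a gap in the plan, not as a demonstrated bias. Membership of the analysis set is settled after the arm is known at the site, and the supplied text provides no means of seeing whether losses differ by arm. That sites are unmasked is inferred from their access to the result and from the absence of any masking beyond block size.

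The effect requires exclusions that differ by arm and relate to prognosis. Under the assumed 16 against 8, false non-inferiority ranges from about 4 to 5% through 6% to 14%, depending only on how the excluded patients fare. If exclusions are few, or unrelated to arm and outcome, the bias is negligible. The actual size cannot be derived because neither the number randomised nor the number without EVAR by arm is given. This is a worthwhile, inexpensive improvement.

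**What to change.** Keep mITT as the primary non-inferiority set, and make these changes:

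1. In section 10.2.1, add a table by arm of patients randomised, patients not in mITT, and the reason.
2. In section 10.1, add a sensitivity analysis of the same risk difference on all randomised patients. Measure time from randomisation for those without EVAR, since they have no day 0. Use known outcomes where available and a tipping-point table over the rest.
3. Report any superiority statement together with the all-randomised result.
4. Reconcile the mITT wordings in sections 10.1 and 12.4 so that a failed delivery converted to open repair stays in the set as a primary-endpoint failure.
5. If a separate SAP already contains the analysis in item 2, cite it in section 10.1 instead.

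The all-randomised result should inform interpretation and need not become a second pass-or-fail test, given the dilution concern.

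The cost is wording and two tables. Assignments are already in the EDC. Section 4.5 specifies follow-up for subjects undergoing EVAR, so outcomes of the others may not exist; the tipping-point table covers that, and no new outcome collection is needed. The result may look slightly less favourable.

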10.2 STATISTICAL METHODS

All non-imaging-driven variables in the composite endpoint will be evaluated to 1 year (day 365 post-implant), whereas imaging-driven variables will be evaluated to a 1-year window (day 365 +/- 60 days). The day of implantation will be set as day 0. Early events are defined as those occurring from the date of the procedure up to 30 calendar days post-operatively. Late events are defined as those occurring from after 30 calendar days post-operatively (from day 31 forward).

The null hypotheses for both non-inferiority and superiority will be evaluated with one-sided alpha levels of 0.05.

If the non-inferiority null hypothesis is rejected, the null hypothesis for superiority will be investigated.

Hypotheses for Non-Inferiority:

Null Hypothesis:

 $H1_0$: $\mu_A - \mu_B \le -8\%$ (AFX is inferior with respect to the primary

endpoint)

Alternative: $H1_1$: $\mu_A - \mu_B > -8\%$ (Statistical evidence of non-inferiority)

Hypotheses for Superiority:

Null Hypothesis: $H2_0: \mu_A - \mu_B \le 0$ (The two device groups have equal effect)

Alternative: $H2_1$: $\mu_A - \mu_B > 0$ (Statistical evidence of superiority)

Data for the primary endpoint will be presented as point estimates for both the treatment (AFX device) and control (proximally fixated devices), along with a 95% confidence interval for the difference. The lower bound of a one sided 95% confidence interval is used to evaluate the non-inferiority and superiority null hypotheses.

Quantitative parameters will be described using the following summary descriptive statistics: number of non-missing values, mean, standard deviation, median, first and third quartiles, and minimum and maximum values.

Qualitative parameters will be described overall using frequencies and percentages. Percentages will be calculated on the number of non-missing observations. In all cases, the number of missing values will be specified.

Kaplan-Meier estimates will be generated for the composite endpoint components across the duration of the trial.

Sample Size Determination:

Given an alpha error rate of 0.05, a desired power of 90%, and assuming a success rate (in terms of the primary endpoint) of 86% for AFX with an 8% advantage over the control group, the sample size required to demonstrate non-inferiority is 154 subjects in total. In order to have enough power to evaluate all hypotheses the sample size for this trial was driven by the evaluation of superiority. In this case, an alpha error rate of 0.05, power of 80%, success rate of 86% for AFX, and a relative 8% advantage in AFX's favor requires 566 patients. A 7% advantage in AFX's favor requires 724 patients. An approximate dropout rate of 10%/1-year indicates 804 patients should be enrolled to provide 724 patients at 1 year. The original protocol thus called for enrollment of up to 800 subjects. The enrollment was completed at 455 subjects after an unplanned analysis supported that the superiority evaluation was futile. With a total of 455 subjects enrolled, 410 are assumed to reach the 1-year endpoint after 10% dropout. This sample size results in 99% power for the non-inferiority test under original assumptions, and thus the trial is considered adequately powered for evaluating non-inferiority. The sample size has been determined with PASS version 12.0.2.

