10.2.2 HANDLING MISSING VALUES

In order to provide unbiased and informative findings, no replacement of missing values is planned for any parameters. In all applicable cases, reported analysis will mention the number of missing values for each outcome in the mITT population.

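### Section 10.2 limits Kaplan-Meier to the ARC components, so five-year mortality and late MAEs fall by default to percentages that ignore censoring

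*Combined protocol and SAP*

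**What the plan says.** Section 6.2 lists as secondary endpoints "Major Adverse Events (MAEs) at 30-Days, 12-Months and annually thereafter, up to five years". All-cause mortality is one of those MAEs. Aneurysm-related mortality is a separate secondary endpoint in the same list.

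Section 10.2 names two ways of summarising outcomes that are followed beyond one year:

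- A general rule: "Qualitative parameters will be described overall using frequencies and percentages", and "Percentages will be calculated on the number of non-missing observations", with the number of missing values stated.
- A specific one: "Kaplan-Meier estimates will be generated for the composite endpoint components across the duration of the trial".

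Section 6.1 lists the components of the composite. The only death among them is peri-operative. Rupture, conversion and reintervention for device- or aneurysm-related complications are also components.

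Section 10.2.2 adds that "no replacement of missing values is planned for any parameters" and promises a count of missing values for each outcome. Section 10.1 refers to a SAP for further information; no separate SAP text is among the documents supplied.

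The only dropout figure is in the sample size paragraph of 10.2: "An approximate dropout rate of 10%/1-year indicates 804 patients should be enrolled to provide 724 patients at 1 year", and later "With a total of 455 subjects enrolled, 410 are assumed to reach the 1-year endpoint after 10% dropout".

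**The concern.** Late all-cause death, late aneurysm-related death, and late myocardial infarction, stroke, renal failure, bowel ischemia and paraplegia are not ARC components. The Kaplan-Meier sentence does not reach them, and the general percentage rule is the only method stated that does.

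A five-year percentage needs a rule for the patient who is lost at, say, year 2 without an event. The plan does not define when such a patient counts as non-missing. If that patient drops out of the denominator while patients with early events stay in, the percentage exceeds the risk. If that patient is kept as event-free, the percentage falls short of it. In both cases the result depends on retention as well as on the device, so two arms with the same risk and different loss will show different percentages. Printing the number missing discloses the problem but does not correct it.

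Loss is a practical matter here. Follow-up is by local standard of care on a schedule that sites may alter (5.8), and 16.1 anticipates visits missed or delayed because of COVID-19. Section 5.8 also has converted patients leave the trial 30 days after conversion, or at discharge if that is later. Their later deaths and MAEs are therefore unobserved by design, and conversion is itself a device outcome that may differ by arm.

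**Working it through.** **1. The plan's own dropout figures.** 724 / 0.90 = 804.4 (804 stated). 455 × 0.90 = 409.5 (410 stated). Both reproduce, and both apply 10% once, to reach one year.

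**2. Assumed inputs.** The documents give no five-year event rate, no dropout after year 1 and no dropout by arm. I take a true five-year risk R = 25%, constant hazards and dropout independent of outcome, and vary the yearly dropout d.

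**3. Formulas.**
- Event hazard h = −ln(1 − R)/5; dropout hazard c = −ln(1 − d).
- Observed events E = h/(h + c) × [1 − exp(−5(h + c))].
- Event-free and still followed at year 5: C = (1 − R)(1 − d)^5.
- Reading A (known status only): E/(E + C). Reading B (losses kept as event-free): E.

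**4. At d = 10%.** h = 0.0575 and c = 0.1054. E = 0.3532 × (1 − 0.4429) = 0.197 and C = 0.75 × 0.5905 = 0.443. Reading A is 0.197/0.640 = 30.8%; reading B is 19.7%. By dropout alone, 455 × 0.5905 = 269 patients would remain at year 5.

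**5. Sensitivity to dropout, true risk 25%.**

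| Dropout | Reading A | Reading B |
|---|---|---|
| 10% every year | 30.8% | 19.7% |
| 5% every year | 27.7% | 22.2% |
| 2% every year | 26.0% | 23.8% |
| 10% in year 1, none later | 25.2% | 22.8% |

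Last row: events in year 1 are 0.3532 × (1 − 0.8497) = 0.0531. Events in years 2 to 5 are 0.8497 × (1 − 0.7944) = 0.1747. Their sum is 0.228. C = 0.8497 × 0.7944 = 0.675, and 0.228/0.903 = 25.2%.

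**6. Sensitivity to the event rate.** At 10% every year, reading A turns true risks of 5%, 10%, 20% and 30% into 6.5%, 12.8%, 24.9% and 36.4%.

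**7. False arm difference.** Equal true risk of 25%, dropout 10% v 5% a year. Reading A: 30.8 − 27.7 = +3.1 points. Reading B: 19.7 − 22.2 = −2.5 points. The sign depends on the undefined denominator.

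**8. Kaplan-Meier on the same data.** In simulation (228 per arm, 10% yearly dropout, 4,000 runs) it returned on average 10.0% and 25.1% for true risks of 10% and 25%.

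**The case against.** **The plan never assigns crude percentages to these endpoints.** The quoted rule is a generic one for describing categorical data, and a SAP is cited for more. This stands. The accurate statement is that the protocol names no estimator for them and the general rule applies by default. If the SAP names one, the two texts need only be aligned.

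**A reader might infer that risk is overstated in both arms by a known amount.** The documents do not support that. The direction turns on an undefined denominator (step 5), and "An approximate dropout rate of 10%/1-year" is a one-year figure; carrying it to year 5 is an extrapolation. If loss stops after year 1, reading A is almost right.

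**A reader might also include AAA-related secondary procedures.** These largely coincide with the ARC component for reinterventions, which already gets Kaplan-Meier, so they do not belong in this point. Aneurysm-related mortality overlaps in part, since death within 30 days of the index procedure is a component; late aneurysm-related death is not.

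**The artefact is small beside sampling error.** In step 7, reading A, known status covers about 0.640 × 228 = 146 and 0.802 × 228 = 183 patients. The standard error of the difference is √(0.308 × 0.692/146 + 0.277 × 0.723/183) = 5.1 points, so 3.1 points is about 0.6 of a standard error. That is fair, but a bias does not average out and is avoidable here.

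**No test is attached to these endpoints, and missing counts will be shown.** Both are true. They limit the consequence without repairing the estimate.

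**Conclusion.** The point holds as a gap in the plan. By default, five-year all-cause mortality, the MAE composite, late non-fatal MAEs and late aneurysm-related mortality would be summarised by percentages that ignore censoring, while the ARC components from the same patients get Kaplan-Meier. For an assumed true risk of 25%, the reported figure would lie anywhere from 19.7% to 30.8% across the dropout patterns examined. The largest errors need 10% loss in every year. With 10% in year 1 only, the range is 22.8% to 25.2%.

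These sizes rest on assumed event rates, constant hazards and loss unrelated to outcome. None of them is a forecast for this trial.

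The endpoints are secondary and carry no hypothesis test. Nothing here bears on the primary one-year comparison. The change should be made because the five-year comparison of the two device concepts depends on these summaries and the cost is slight.

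**What to change.** In 10.2 (and in the SAP, if it is silent):

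- Extend Kaplan-Meier by arm, with numbers at risk and 95% confidence intervals, to all-cause mortality and to the MAE composite, which contains death.
- Use cumulative incidence for aneurysm-related mortality, with other-cause death as the competing event. Use it also for the non-fatal MAEs that can occur late (myocardial infarction, stroke, renal failure, bowel ischemia, paraplegia), with death as the competing event.
- Leave the procedure-bound MAEs, blood loss and respiratory failure, as percentages; annual curves would add nothing.
- Define when an observation counts as non-missing for any percentage that remains.
- Report length of follow-up and loss by arm.
- State that exit after conversion is potentially informative censoring, which Kaplan-Meier alone does not correct.

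The cost is SAP wording and standard SAS procedures. Event and last-contact dates are already needed for the planned component curves, so no new data are required.
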